13.2 Analysis plan

13.2.1 Microbiome

The microbial data may be over-parameterised depending on the taxonomic level at which analysis is carried out. At a strain level we will have more microbial strains present in samples than there will be samples taken. However, due to current limitations in sequence read length we have shown that at an Operation Taxonomy Unit (OTU) level (that is sequences with >97% similarity which corresponds to species level), we identify considerably less OTU (138) after normalisation than samples forecast for the proposed study[19]. We will use multivariate ordination techniques to summarise the major trends in variation in bacterial community composition of infant stool and will allow us to identify those taxa most closely associated with changes in the pattern of bacteria over time. We will then use canonical ordination to quantify the impacts of the diet on the microbiome composition.

13.2.2 Body Composition

Continuous variables that follow an approximately normal distribution will be summarised using the mean and standard deviation. Skewed continuous variables will be summarised using the median and inter-quartile range. Categorical variables (binary, ordered and multinomial) will be presented in terms of frequencies and percentages. This will be an intention to treat analysis, infants will be analysed in accordance with the treatment to which they are randomised. For outcomes measured on a single occasion, a multiple regression model containing the treatment variable, stratifying variables (gestational age and birth weight), sex and postmenstrual age at time of measurement will be used to estimate the effect of the intervention.

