1. PROTOCOL SUMMARY

Title (Acronym)	In teractions between the di et and g ut microbes, metabolism and body composition in preterm infants (INDIGO)
Study centres	Newcastle Royal Infirmary and Chelsea and Westminster NHS Foundation Trust (Imperial College London). Additional sites may be added
Study objectives	To evaluate whether an exclusive human milk diet compared with exposure to cow's milk-based products results in differences in a) gut bacteria (types and diversity, b) stool and urine metabolites and c) body composition
Study design	Randomised open label, controlled trial
Study population	 Inclusion criteria Preterm infants born below 30 completed weeks of gestation (≤ 29 weeks and 6 days) <72 hours age Written informed consent from parents Exclusion criteria Major congenital or life-threatening abnormalities Inability to randomise within 48 hours of birth Exposure to bovine milk product prior to randomisation Likelihood of transfer to another hospital before 34 weeks postmenstrual age
Interventions	• Exclusive human diet (human donor milk and human milk-based fortifier: 'Prolacta RTF 26' and 'Prolacta 6')
Route of administration	Enteral
Target number of patients	At least 100 patients to provide ~80 evaluable infants in total with stool samples for microbiome analysis at 34w PMA
Randomisation	 Using minimisation incorporating the following variables: hospital site, gestation (<25 weeks: ≤24 weeks and 6 days), and multiple birth status Secured, password protected web-based randomisation using minimisation algorithm (www.sealedenvelope.com or similar)
Primary outcomes	 Microbiota: gut bacterial diversity, proportions of specific taxa, e.g. Bifidobacteria species Body composition; adipose tissue mass and non-adipose tissue mass assessed using whole body magnetic resonance imaging (MRI) at term (37-42 weeks postmenstrual age)
Secondary outcomes	Metabolome: Gut derived metabolites and markers of gut function; metabolites include stool Volatile Organic Compounds (VOC, using Gas Chromatography MS), and urine (e.g. using 1H NMR and/or Liquid Chromatography MS); markers of gut health may include those measured in the stool (e.g. calprotectin) and urine (e.g. intestinal fatty acid binding protein, iFABP) Feed and nutrition related outcomes Healthcare resource use Neonatal morbidities and clinical outcomes Adipose tissue volume and distribution
Duration of trial intervention	To 34 weeks postmenstrual age

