9.5. Randomisation

Infants will be randomised using minimisation incorporating the following variables: hospital site, gestation (<25 weeks: ≤ 24 weeks and 6 days), and multiple birth status; this will be held and coordinated by the Newcastle research team using an internet based secured randomisation system, and will include strata for hospital site, gestation (<25 weeks and ≥ 25 weeks gestation), and multiple birth status. Contact and allocation will be by password protected internet access. Infants will be allocated to either standard diet (control) or the exclusive human milk-based diet (intervention). Multiples (twins and higher order) will be randomised independently.

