11.4.5 Body composition (Chelsea & Westminster site only)

We will use whole-body MR imaging to obtain serial axial images (5mm slice and inter-slice thickness) to quantify total adipose tissue (AT) volume as the sum of 6 discrete depots: superficial subcutaneous abdominal, superficial subcutaneous non-abdominal, deep subcutaneous abdominal, internal abdominal (IA), and internal non-abdominal, as previously described (Modi et al. 2009).[11] Image analysis with the use of Slice-OMatic (Tomovision) will be undertaken independently blinded to participant identity and group allocation. AT volume in litres will be converted to AT mass in kg, assuming a value for the density of AT of 0.90 kg/L. Non-AT mass is calculated by subtracting AT mass from the weight of the infant on the day of the MR scan using the following formula: [body weight (g) - [AT volume (cm³) × 0.9]]. MR scanning will be carried out in natural sleep between 37-42 weeks postmenstrual age.

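### The body composition model names birth weight as a stratifying variable, which it is not, and leaves out multiple birth status, which is a minimisation factor

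*Protocol*

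**What the plan says.** Section 9.5 describes allocation by minimisation and says that the web system "will include strata for hospital site, gestation (<25 weeks and ≥ 25 weeks gestation), and multiple birth status". The protocol summary (section 1) gives the same three factors. Neither place mentions birth weight, which appears in section 11.3.2 only as a baseline measurement. Section 9.5 adds: "Multiples (twins and higher order) will be randomised independently".

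The model in section 13.2.2 is introduced with "For outcomes measured on a single occasion, a multiple regression model containing the treatment variable". The other terms are "stratifying variables (gestational age and birth weight), sex and postmenstrual age at time of measurement". Multiple birth status and site are not among them.

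Body composition by MRI at term-equivalent age is a primary endpoint (section 8.1.2). It is measured at Chelsea and Westminster only (sections 8, 11.2.4 and 11.4.5). Section 13.1.2 plans 20 infants per group for 80% power, two-sided 5%, to detect 0.42 kg in non-adipose tissue mass with an SD of 0.46 kg.

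**The concern.** The protocol gives two different accounts of which variables were balanced by design. Section 13.2.2 tells the analyst to adjust for the stratifying variables and then, in brackets, lists a set that is not the one used. Both cannot be followed. One analyst would go by the term and put in multiple birth status. Another would go by the bracket and leave it out. In an open-label trial that choice should be fixed before outcome data are seen, and a later plan that copies the bracket would copy the error.

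The statistical stake is precision. Balancing a factor makes the treatment estimate less variable if the factor predicts the outcome. A model without the factor leaves its variance in the residual, so the reported standard error exceeds the true one. Confidence intervals are then too wide and the test rejects too rarely.

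**Working it through.** **1. Factor by factor, for the MRI model**

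| Variable | Minimised on (sections 1, 9.5) | In the 13.2.2 model | Effect |
|---|---|---|---|
| Hospital site | yes | no | none: one site only |
| Gestation | yes, cut at 25 weeks | yes, as gestational age | covered |
| Multiple birth status | yes | no | the gap |
| Birth weight | no | yes, called stratifying | wrong label, acceptable covariate |
| Sex, postmenstrual age at measurement | no | yes | acceptable covariates |

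The mismatch for this endpoint comes down to multiple birth status.

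**2. The protocol's own sample size figure**

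Inputs from section 13.1.2: difference 0.42 kg, SD 0.46 kg, n = 20 per group.
- Standardised difference: 0.42/0.46 = 0.913. Standard error: 0.46 × √(2/20) = 0.1455 kg. Ratio: 0.42/0.1455 = 2.887.
- Power is 0.803 by two-sample t-test and 0.823 by normal approximation. The stated 20 per group for 80% power reproduces. It uses no covariates, so the disputed list does not affect it.

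**3. Large-sample consequence of leaving the factor out**

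Let R² be the share of outcome variance due to multiple birth. The protocol gives no value, so 0, 5, 10 and 20% are assumed, with perfect balance between arms.
- Model SE / true SE = k = 1/√(1 − R²).
- Actual type I error of the nominal 5% test = 2 × [1 − Φ(1.96 k)].
- Power uses the noncentral t with 38 degrees of freedom and noncentrality 2.887 k. With the factor included, the critical value is the usual t. With it omitted, the critical value is k times that.

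| R² | k | Type I error, omitted | Power, omitted | Power, included |
|---|---|---|---|---|
| 0 | 1.00 | 0.050 | 0.80 | 0.80 |
| 5% | 1.03 | 0.044 | 0.81 | 0.82 |
| 10% | 1.05 | 0.039 | 0.82 | 0.84 |
| 20% | 1.12 | 0.028 | 0.83 | 0.88 |

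Example at 20%: k = 1/√0.8 = 1.118; 1.96 × 1.118 = 2.191; two-sided tail 0.028.

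**4. Simulation at the planned size**

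Perfect balance is optimistic with 40 infants, so minimisation on multiple birth and gestation below 25 weeks was simulated and the 13.2.2 model fitted with and without a multiple birth term (4,000 runs per scenario). Assumed, since the protocol does not give them: 30% of infants are multiples; the effect of multiple birth is 0, −0.5 or −1.0 residual SD; sibling correlation is 0 or 0.5; the favoured arm is chosen with probability 0.8.

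| Sibling correlation | Multiple birth term | Model SE / true SE | Type I error |
|---|---|---|---|
| 0 | omitted | 0.98 to 1.06 | 0.035 to 0.051 |
| 0 | included | 0.98 to 0.99 | 0.049 to 0.056 |
| 0.5 | omitted | 1.03 to 1.10 | 0.030 to 0.040 |
| 0.5 | included | 1.02 to 1.03 | 0.041 to 0.042 |

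For scale, with 30% multiples an effect of 1.0 residual SD is R² = 0.21/(1 + 0.21) = 17%, and an effect of 0.5 is 0.0525/1.0525 = 5%. The worst case is a standard error 6% too large without sibling correlation and 10% too large with it. In the latter case, 2 to 3% remains after the term is added and is due to the siblings, not to the omitted factor.

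**The case against.** The strongest reply is that little follows from the slip. Gestational age is in the model, site cannot vary, and adjusting for birth weight does no harm. The one missing factor matters only if it is prognostic beyond the covariates already there; if gestational age and birth weight carry part of its effect, the remaining share is smaller than its raw share. The bias is conservative, the R² values have no source in the document, and the trial calls itself mechanistic and exploratory. All of this stands. It limits the size of the point but does not remove the contradiction, because section 13.2.2 does not leave the covariates open for a later plan: it names them, and names them wrongly.

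Three stronger readings are tempting and are not supported.
- A reader might infer that the trial's error bars in general do not match its randomisation. The table of factors shows one missing term in one model.
- A reader might infer that the planned 80% power is lost. It is not: with the factor omitted, power stays at 0.80 or above under these assumptions. What is given up is the gain that adjustment would bring.
- A reader might infer that the microbiome analysis is unadjusted, since section 13.2.1 says only "We will then use canonical ordination to quantify the impacts of the diet on the microbiome composition" and names no minimisation factor. But it names no test either, and does not say that nothing will be conditioned on. Covariates for an ordination are commonly left to the statistical analysis plan, which is not shown, so silence there is not an error in the protocol.

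**Conclusion.** The contradiction is certain and rests on the text alone: birth weight is not an allocation factor, and multiple birth status, which is one, is absent from the model for a primary endpoint. The consequence is modest and goes in the conservative direction. For R² of 5 to 20%, the nominal 5% test runs at about 0.044 to 0.028, and roughly 1 to 5 percentage points of power are forgone at 20 per group. If multiple birth does not predict body composition, the effect is nil. These sizes depend on assumed R², share of multiples, sibling correlation and quality of balance, none of which the protocol supplies. There is no inflation of false positives, and the sample size needs no change. The wording should be corrected before analysis.

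**What to change.** In section 13.2.2, replace the bracketed list with the actual minimisation factors: gestational age and multiple birth status, plus site only for outcomes to which more than one site contributes (it is constant for MRI). Keep birth weight, sex and postmenstrual age at measurement as named prognostic covariates, no longer described as stratifying.

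The cost is one degree of freedom in the MRI model. With 40 infants, the model as written has six parameters including the intercept and leaves 34 residual degrees of freedom; the corrected one leaves 33. Recruitment, procedures and sample size are untouched. Multiple birth status must already be entered for the minimisation to run, but it is not in the data lists of section 11.3 and should be added there so that it reaches the analysis dataset.

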13.2.3 Data queries, missing data

Owing to the nature of this study, it is expected that a number of infants will not have blood sampling conducted or attend the end-of study MR scan (primarily due to the death, ill-health, or withdrawal of the subject). As far as possible, reasons for non-attendance will be recorded. Where infants are transferred to other hospitals before the end of the study intervention (34 weeks corrected age) or before discharge home, the investigators will make contact with that hospital and arrange to collect data. The data collected will already form part of the infants' medical record and can be extracted from clinical records or clinical databases e.g. the National Neonatal Research Database that holds data from the Badger system. The data will include feeding information (e.g. type of milk and supplements), growth (e.g. weight, length and head circumference), any important medical outcomes (e.g. infection episodes, requirement for respiratory support) and duration of hospital stay.

14 REGULATORY AND ETHICAL CONSIDERATIONS

The trial will require approval by a Research Ethics Committee. We do not consider the trial poses any significant risks or any additional risk or discomfort over and above that already associated with neonatal care. The control arm represents standard UK practice and involves a range of products and milks (MOM, preterm-formulated formula milk and fortifier). The trial intervention involves MOM, donor human milk and human milk derived fortifier produced commercially. This study is an exploratory trial of the mechanisms of action of two milk-based dietary regimes on the pattern of gut bacteria, and is not a Clinical Trial of an Investigational Medicinal Product (CTIMP) according to MHRA definitions because it is a food product and/or supplement that is not presented as a medicine.

(https://www.gov.uk/government/uploads/system/uploads/attachment_data/file/317952/Algothrim.pdf)

- The preterm formulae and cow's milk derived breast milk fortifiers used will be the same as used clinically on UK neonatal units (SMA Gold Prem 1, Nutricia Nutriprem 1, Nutriprem breast milk fortifier).
- The trial will be supported by experienced, GCP trained research teams at both sites with substantial expertise in the care of newborn infants and neonatal nutrition research. There is

836	minimal discomfort associated with obtaining blood samples, but these will only be taken
837	when blood is required for clinical reasons. Parents will have the opportunity to decline blood
838	sampling and MRI. A parent information leaflet will be provided, and signed parental consent
839	will be obtained. Biological sample collection and storage will be conducted according to
840	existing SOP of the research team and sponsor.

842 15 TRIAL ORGANISATIONAL STRUCTURE AND RESPONSIBILITIES

- 843 15.1 Trial sponsor
- The institution employing the chief investigator (Newcastle Hospitals NHS Foundation
- 845 Trust) will act as sponsor
- 846 15.2 Trial steering committee
- A Study Steering Committee (SSC) will be established to oversee the conduct of the study. It
- is anticipated that the SSC will comprise the lead investigators, an independent chair,
- additional independent members and a user representative. The SSC will meet thrice during
- the course of the study, once shortly after the start of the study and then annually or as
- required throughout the course of the study.
- 852 15.3 Data monitoring and ethics committee
- This is a mechanistic study in which trial outcomes will not be analysed until study end. In
- addition, the dietary regimens used are un-blinded. We therefore do not plan to have a Data
- 855 Monitoring and Ethics Committee
- 856 15.4 Trial management
- The trial will be reviewed by the trial management group (TMG) at the end of an internal
- pilot phase (n=5 per trial arm at each site) and key data reviewed. The TMG will consist of
- 859 the key investigators [name] along with trial managers, and research nurses, and
- 860 will meet by teleconference every 3 months, with more frequent meetings if needed in the set
- up and initial period of recruitment.
- 862 15.5 Trial registration
- 863 The trial will be registered on the International Standard Randomised Clinical Trial Number
- 864 registry.
- 865 **15.6** Trial sites

866	Two large tertiary neonatal units with considerable experience of intervention trials in high
867	risk neonates: Royal Victoria Infirmary, Newcastle upon Tyne, UK and Chelsea &
868	Westminster Hospital (Imperial College), London, UK. Further sites with necessary research
869	infrastructure may be added later. Protocol modification August 2018: addition of two
870	additional NICU sites at James Cook University Hospital, Middlesbrough, UK and William
871	Harvey Hospital, East Kent, UK.
872	
873	15.7 Investigator responsibilities
874	Investigators will be responsible for ensuring that institutional (site specific) approval has
875	been obtained as well as Agreements signed off by their Institution prior to the start of the
876	study. Investigators are required to ensure compliance to the Clinical Trial Protocol,
877	Investigators File and any other study instructions as required by the Sponsor or its
878	representatives. Investigators are required to ensure the accuracy of the trial data according to
879	the instructions provided. Investigators are required to allow access to study documentation
880	or source data on request for monitoring visits and audits performed by, the Sponsor or any
881	regulatory authorities. The Investigator may appoint co-investigators to assist with conduct of
882	the study locally. All co-investigators must be listed as members of the research team and
883	appropriately trained. The Investigator has overall responsibility for ensuring the conduct of
884	the study locally.
885	
886	16 END OF TRIAL
887	The end of trial will be declared when the last infant recruited completes the last follow-up

999	without absent / reversed EDF. merease by 13 mi/kg twice a day (BD)	
1000	Infants $32^{+0} - 33^{+6}$ weeks GA	
1001	With absent / reversed EDF: increase by 15ml/kg/day OD	
1002	Without absent / reversed EDF: increase by 30ml/kg/day OD	
1003		
1004	In all babies, irrespective of gestational age or Dopplers, once 60 ml/kg /day of enteral feeds	
1005	are tolerated consider going up 15 ml / kg twice a day.	
1006	4. Feed Intolerance	
1007	Withdrawal of feeds should be considered if:	
1008	- the pre-feed gastric aspirate exceeds 4ml/kg	
1009	- there are possets or vomits after two consecutive feeds	
1010	- there is marked or tender abdominal distension or the presence of visible bowel loops	
1011	- there is heavy bile staining of gastric aspirate or bilious vomiting	

1012

Figure 1: Summary of Enteral feeding initiation and advancement

In all babies, once 60 ml/kg /day of enteral feeds are tolerated consider going up 15 ml / kg twice a day.

1013

1014 Feed advancement guideline (Newcastle Hospital) 1015 1016 1017 Summary (enteral feed guidelines last updated August 2016) 1018 1019 1020 Summary recommendations relating to feed advancement for infants ≤34 weeks and 1021 ≤1750g birthweight 1022 Start feeds early in all infants except where there are particular concerns – if the mother 1023 plans to provide EBM but none is available wait at least 48 hours before starting formula Use fresh colostrum as soon as it is available – use for mouthcare or give as bolus via 1024 NG unless specifically contra-indicated 1035 Encourage the use of expressed breast milk (EBM). Speak to all mothers and 1027 1028 emphasise the numerous benefits of EBM. Babies who are born with Absent or Reversed End Diastolic Flow may also be suitable 1029 1030 for early feeds 1031 Ventilation or the presence of umbilical catheters *per se* are not contraindications. 1032 Start at a volume of 10-20mls/kg/day 1033 If feeds tolerated advance at 24mls/kg/day (= increase of 1ml/kg/hour every day or 0.5ml/kg/hour twice a day). 1036 If there is no EBM use Gold Prem 1 (GP1) or Nutriprem 1 to initiate feeds unless in trial 1038 Use breast milk (or GP1 or NP1) as the only milk until full enteral feeds are tolerated 1020 Use oro-gastric tubes in preference to nasogastric tubes 1042 1043 Use continuous feeds until 28-30 weeks corrected gestation
